#### 6.1.7 Visit 7: Postoperative Day 18 ( $\pm 1$ Day) (Post-treatment exam)

***NOTE: Post-surgery visits should be scheduled so that IOP can be assessed within  $\pm 2$  hours of the time of IOP assessment on Visit 1.***

- Perform a urine pregnancy test, as applicable
- Perform a clinical assessment of ocular symptoms
- Perform assessment of pin-holed Snellen VA
- Perform biomicroscopy assessment
- Perform IOP measurement
  - IOP should be assessed within  $\pm 2$  hours of the time IOP was assessed at Visit 1 (Screening). Measurement of IOP must occur after the assessment of ocular symptoms and biomicroscopy.
- Collect AEs and changes in concomitant medications
- Exit the subject from the study

#### 6.1.8 Unscheduled Visits

Additional visits may be scheduled, as necessary, to ensure the safety and well-being of subjects. All additional exams should be fully documented in the source documents and on Unscheduled Visit eCRFs, as appropriate. Visits intended to fulfill scheduled visit requirements that fall outside the designated scheduled visit range, are not Unscheduled Visits. In these cases, the visit data will be collected and transcribed to the appropriate scheduled visit eCRF.

If a subject is seen for multiple visits within a given visit timeframe, the data from the visit that are intended to meet protocol requirements for the scheduled visit should be captured on the visit eCRF. Where such a determination cannot be made, the first visit within the scheduled visit interval will be used for completion of the protocol-required scheduled visit eCRF. Data from any additional visits within a scheduled visit interval will be captured on an Unscheduled Visit eCRF.

### 6.1.9 Missed Visits

If a subject misses any scheduled follow-up visit and cannot be seen prior to the start of the allowed visit range for the next scheduled follow-up visit, the visit is considered missed.

## 6.2 Study Completion

Bausch + Lomb Clinical Operations will notify the Investigator of when to contact the IRB/EC to inform them that the study is complete.

### 6.2.1 Early Study Termination

If during the study it becomes evident to the Sponsor that the study should be stopped prematurely, the study will be terminated and appropriate notification will be given to the Investigator(s), IRB, and FDA. Bausch + Lomb will instruct the Investigators to stop dispensing study materials and to arrange for study closeout at each site.

### 6.2.2 Subject Completion

A subject has completed the study when Visit 7 has been completed and the subject has been exited. Subjects who require further follow-up for an AE will be followed according to [Sections 7.3 and 7.4](#).

NOTE: If rescue is required at Visit 7 and all assessments have been completed the subject has completed the study and can be exited.

### 6.2.3 Subject Discontinuation

A subject MAY be discontinued (at the discretion of the Investigator, the Sponsor and/or the IRB/EC) prior to the final study visit for several reasons, including, but not limited to:

- A serious adverse event (SAE) occurring during the course of the study, which precludes continued treatment or follow-up
- The subject not following required study procedures
- If a subject exhibits intolerable adverse events (AEs, related or not related to the study treatment), or if a subject fails to show improvement in inflammation or the clinical status of inflammation worsens, the treating Investigator may opt to withdraw the subject from the trial and implement necessary intervention (ie, rescue therapy)

A subject MUST be discontinued prior to the final study visit for any of the following reasons:

- Voluntary withdrawal
- Death
- Pregnancy
- Rescue Medication
- Investigator decision that it is not in the best medical interests of the subject to continue participation in the investigation

Prior to discontinuing a subject, every effort should be made to contact the subject, schedule a final study visit (see Appendix A, Early Discontinuation visit), obtain as much follow-up data as possible, and to retrieve all study materials. Adverse events will be followed as described in [Sections 7.3](#) and [7.4](#). An early termination visit should take place within 7 days following the subject being discontinued. If a subject is discontinued during a given scheduled visit, the early termination procedures as outlined in Appendix A may be performed at that visit. Subject withdrawals will be documented clearly on the source document and applicable electronic case report form (eCRF).

Notification of subject discontinuations will be made to the Sponsor. Any subject discontinued from the study will not be replaced.

#### 6.2.3.1     Rescue Medication

Subjects will be assessed at Visits 4 through 7 (Postoperative Days 3, 8, 15, and 18) for treatment rescue. Subjects with worsening or no change in the grade of inflammation in the study eye compared with the previous visit are eligible and may be considered for rescue medication. For subjects who meet either of these criteria, it is at the discretion of the Investigator when to begin rescue medication. The choice of rescue medication and dosing shall also be determined by the Investigator. Subjects requiring rescue medication for inflammation will stop treatment with the study drug and will be promptly discontinued from the study. The inflammation will not be reported as an adverse event (AE). The rescue medication will be recorded on the Concomitant Medication electronic case report form (eCRF) and the exit reason will be entered as “rescue medication” in the eCRF. Subjects who receive rescue medication will be counted as treatment failures as of the date of receiving rescue medication. Subjects who require rescue medication should return within 7 days following the date that rescue medication begins in order to undergo the procedures for the early termination visit.

NOTE: Rescue med that is required at V7 will not be recorded on the ConMed eCRF

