### 6.3.2 Disallowed Therapy

A disallowed medication may be administered in an emergency if the subject's safety is in jeopardy. If possible, the Medical Monitor should be consulted prior to administration of the disallowed medication (if not feasible, then as soon as possible afterwards) to determine whether the subject may continue in the study.

If a subject has taken any disallowed medication for any reason other than rescue therapy, record this as a protocol deviation and immediately contact Bausch + Lomb.

Disallowed medications include, but are not limited to the following:

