**Table 2: Disallowed Therapies**

Medication/Class of Drug	Status
Acetylsalicylic Acid > 81mg/day	Excluded starting 2 days before surgery and through 18 days after surgery
Antihistamines (H-1 Antagonist), systemic or ocular	Excluded starting 2 days before surgery and through 18 days after surgery
Artificial Tears	Excluded starting 7 days before surgery and through 18 days after surgery
Biologic Agents (example: anti-TNF- $\alpha$ [eg, Cimzia])	Excluded starting the day of surgery and through 18 days after surgery
Corticosteroids/Glucocorticoids: systemic, inhaled, or ocular	Excluded starting 14 days before surgery and through 18 days after surgery
Decongestants, systemic or ocular	Excluded starting 2 days before surgery and through 18 days after surgery
Flomax (tamsulosin)	Excluded starting 7 days before surgery and through 18 days after surgery
Hydrocodone/Opioid-Based Pain Medications	Excluded starting the day of surgery and through 18 days after surgery (can be used ONLY during surgery)
Ocular Hypotensive Medication, oral (eg, Diamox)	Excluded except for use during IOP one-time intervention at V3
Ocular Hypotensive Medication, topical (eg, Betaxolol)	Excluded except for use during IOP one-time intervention at V3
Immunosuppressants, systemic or ocular	Excluded starting 30 days before surgery and through 18 days after surgery
Mast cell Stabilizers, systemic or ocular	Excluded starting 2 days before surgery and through 18 days after surgery
Methotrexate/DMARDs	Excluded starting 30 days before surgery and through 18 days after surgery
NSAIDs and COX-2 Inhibitors, systemic or ocular	Excluded starting 2 days before surgery and through 18 days after surgery
Plaquinil/Anti-malarial drugs	Excluded starting 30 days before surgery and through 18 days after surgery
Propoxyphene	Excluded starting 2 days before surgery and through 18 days after surgery
Serratiopeptidase	Excluded starting 7 days before surgery and through 18 days after surgery

Abbreviations: COX, cyclooxygenase; DMARD, disease-modifying anti-rheumatic drugs; TNF, tumor necrosis factor.

**Additionally, any medication the subject uses that the Investigator and/or Medical Monitor feels may interfere with subject safety or study parameters should be considered a disallowed medication.**

Disallowed medication that is used for persistent or worsening inflammation is called “Rescue Medication” and is discussed in [Section 6.2.3.1](#). Subjects taking rescue medication must stop

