#### **6.4 Treatment Compliance**

Any subject who does not follow instructions to a degree that, in the opinion of the Sponsor or the Investigator, jeopardizes the subject's well-being or the validity of the study, must be discontinued.

Subjects will be given study drug administration diaries to record the date and time of each study medication instillation. Treatment compliance during the study will be documented by subject entries in the study diaries. Study personnel will instruct the subject to bring the study diary to each of their follow-up visit(s) and remind subjects that no information other than dosing information should be recorded in the diary.

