#### 8.5.1.1 Efficacy Endpoint Analyses

##### Analysis of Primary Efficacy Endpoints

The primary efficacy endpoints are the proportion of subjects with complete resolution of AC cells at Visit 5 (Postoperative Day 8) and the proportion of subjects with Grade 0 pain at Visit 5 (Postoperative Day 8). Primary efficacy analyses will be based on the intent-to-treat (ITT)

population with missing data imputed as failures (subjects placed on rescue medication prior to the visit being summarized will also be considered failures).

The primary efficacy analyses of the difference between each active treatment group and the combined vehicle treatment group at (Visit 5) Postoperative Day 8 will be tested using Pearson Chi-squared tests with p-values adjusted using a Bonferroni-based tree gatekeeping strategy with the structure shown in Table 3. Null hypotheses with adjusted p-values  $\leq 0.05$  will be rejected.

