### 8.5.9 Missing Data

For the primary efficacy endpoints analyzed using the ITT analysis population, missing data for a subject and data from subjects discontinuing the study or treatment for any reason prior to Visit 5 will be imputed as treatment failures. These analyses will secondarily be presented using LOCF.

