### 1.0 OCULAR SYMPTOMS

*The ocular symptoms of ocular pain, photophobia, itching, tearing, and ocular discharge are all to be graded by subjects using the following ordinal scales:*

**Ocular Pain:** *A positive sensation of the eye, including foreign body sensation, stabbing, throbbing, or aching.*

0 =	None:	Absence of positive sensation.
1 =	Minimal:	Presence of mild sensation or discomfort typical of postoperative ocular surgery (eg, diffuse or focal foreign body sensation, mild transient burning or stinging, etc.)
2 =	Mild:	Mild, tolerable aching of the eye.
3 =	Moderate:	Moderate aching sufficient to require the use of over the counter (OTC) acetaminophen.
4 =	Moderately Severe:	More prolonged aching requiring the use of an OTC analgesic other than acetaminophen.
5 =	Severe:	Intense ocular, periocular or radiating pain (eg, constant or nearly constant sharp stabbing pain, throbbing or aching, etc.) requiring prescription analgesics.

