## **2.0 STUDY DRUG SENSATION ASSESSMENT**

Subject self-reported study drug sensation assessment at Visit 5 should describe the subject's overall or summary impression from Visit 3 through the day before Visit 5 for the degree of discomfort experienced immediately (ie, within 1 minute) after administering study drug. Study drug sensation will be graded on the following ordinal scale:

0 = None: No discomfort from the study drug.  
1 = Mild: Mild discomfort from the study drug.

2 = Moderate: Moderate discomfort from the study drug.

3 = Severe: Severe discomfort from the study drug.

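### Rescue is defined by inflammation only, so a subject who takes a disallowed analgesic for study-eye pain before Visit 5 and stays in the study can count as a success on the primary pain endpoint

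*Combined protocol and SAP*

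**What the plan says.** **Who is rescued.** Section 6.2.3.1 sets the criterion: "Subjects with worsening or no change in the grade of inflammation in the study eye compared with the previous visit are eligible" for rescue, at the Investigator's discretion. Rescued subjects stop study drug, leave the study and are failures from the date of rescue. The text after Table 2 in Section 6.3.2 agrees: "Disallowed medication that is used for persistent or worsening inflammation is called" rescue medication. Neither place mentions pain.

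**Other disallowed use.** Table 2 disallows NSAIDs and COX-2 inhibitors, acetylsalicylic acid above 81 mg/day, opioids (outside surgery) and propoxyphene through 18 days after surgery. When such a drug is taken for another reason, Section 6.3.2 says: "If a subject has taken any disallowed medication for any reason other than rescue therapy, record this as a protocol deviation". The sponsor is then contacted. For emergency use, the Medical Monitor is consulted on whether the subject can stay in.

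**What counts as failure.** The pain endpoint in 8.1.1 is Grade 0 in the study eye at Visit 5, with no condition on analgesic use. Section 8.5.1.1 imputes missing data as failure and adds that "subjects placed on rescue medication prior to the visit being summarized will also be considered failures". Section 8.5.9 adds that "data from subjects discontinuing the study or treatment for any reason prior to Visit 5 will be imputed as treatment failures".

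**The concern.** The plan treats the need for another anti-inflammatory drug as failure of the study drug. It has no matching rule for the drugs that act most directly on its other primary endpoint, pain. A Grade 0 reached with the help of an NSAID or opioid is credited to the assigned arm.

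The direction of the resulting bias is not known. More such use on vehicle raises the vehicle success rate and understates the benefit of LE gel; more use on LE gel overstates it. The LOCF presentation in 8.5.9 does not help, because the Visit 5 grade is observed. Whether such a subject stays in the study is decided case by case at up to about 60 sites, so like subjects can be scored differently.

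**Working it through.** **1. Following one subject through the text.** A randomized subject takes ibuprofen for study-eye pain on Day 5 and reports Grade 0 at Visit 5.
- Rescue (6.2.3.1, 6.3.2): no, because the drug was not taken for inflammation.
- Missing at Visit 5 (8.5.1.1): no.
- Discontinued before Visit 5 (8.5.9): only if someone chose to withdraw the subject.
- Analysis set (8.4): ITT keeps all randomized subjects.
- Result: a protocol deviation, and a success on pain.

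**2. Do other provisions close the gap?**
- *Section 6.2.3* lets the Investigator withdraw a subject for intolerable adverse events and give rescue therapy. A subject withdrawn before Visit 5 is a failure, but the step is optional.
- *Section 6.3.2* has the Medical Monitor judge continuation after emergency use. This is also case by case.
- *Section 6.4* says a subject whose non-adherence is judged to jeopardize the subject's "well-being or the validity of the study, must be discontinued". This turns on the opinion of the Sponsor or Investigator.
- *Exclusions 16, 17 and 23* deal with current or expected need at entry. They do not cover need that arises after surgery.
- *Pain scale (Appendix B, 1.0).* Grade 4 is "More prolonged aching requiring the use of an OTC analgesic other than acetaminophen", and Grade 5 is tied to prescription analgesics. Continuing need at Visit 5 should therefore not be graded 0. The scale does not say how to grade pain that a drug is suppressing at the visit, or how to treat earlier use. It states no recall period, whereas the drug-sensation item asks for the "overall or summary impression from Visit 3 through the day before Visit 5".
- *Per-protocol set (8.4)* is supportive. It may drop such subjects but does not fail them.

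**3. The plan's own power.** Inputs from 8.3: 196 per group, two-sided 0.025; pain 0.739 vs 0.486; AC cells 0.283 vs 0.143. The two-proportion chi-squared formula (pooled variance, no continuity correction) gives 99.9% for pain (plan: 99%) and 87.7% for AC cells (plan: 87%). Both stated figures are sound.

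**4. Size of the effect on pain.** Let U be the share of an arm that takes such a drug for study-eye pain before Visit 5 and stays in. U is an assumption, taken as 2% to 5% (about 4 to 10 of 196). The planned rates are treated as scored under the current text, because the scoring rule of the four earlier studies is not given.

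If users are Grade 0 at their arm's planned rate p, the rate with users failed is p × (1 − U). If every user is Grade 0, it is p − U.

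| U, LE / vehicle | Users' Grade 0 rate | LE vs vehicle, users failed | Difference (points) | Change from 25.3 | Power |
|---|---|---|---|---|---|
| 2% / 2% | arm rate | 72.4% vs 47.6% | 24.8 | −0.5 | 99.8% |
| 5% / 5% | arm rate | 70.2% vs 46.2% | 24.0 | −1.3 | 99.6% |
| 2% / 5% | arm rate | 72.4% vs 46.2% | 26.3 | +1.0 | 99.9% |
| 5% / 2% | arm rate | 70.2% vs 47.6% | 22.6 | −2.7 | 99.1% |
| 2% / 5% | all | 71.9% vs 43.6% | 28.3 | +3.0 | >99.9% |
| 5% / 2% | all | 68.9% vs 46.6% | 22.3 | −3.0 | 98.9% |

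If use is equal and every user is Grade 0, the difference does not move (for 2%: 71.9 − 46.6 = 25.3).

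If instead the planned rates already score users as failures, the current text adds them back. Adding 2 points to LE and 5 to vehicle gives 75.9% vs 53.6%, a difference of 22.3 points, with power 99.3%.

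**The case against.** **The scale already covers much of this.** A subject who still needs an NSAID or opioid at Visit 5 is Grade 4 or 5 by the anchors. That stands. What remains is pain suppressed at the visit, and earlier use that has stopped. For stopped use, one can argue that Grade 0 at Day 8 is a true success on a point-in-time endpoint, and that keeping deviators at their observed value is a recognised ITT choice. This is a fair estimand argument. Against it, the plan already fails rescued subjects from the date of rescue, whatever their later state. The proposed rule applies the same logic to pain.

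**Withdrawal routes exist.** A reader might infer that every analgesic user stays in and is scored a success. The documents do not support that: 6.2.3, 6.3.2 and 6.4 can each lead to withdrawal, and withdrawal before Visit 5 is a failure. The gap concerns only those kept in.

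**The same logic might seem to call for failing NSAID users on AC cells.** It is true that an NSAID user with a cell score of 0 is a success under the current text. But failing a subject with no cells at Day 8 because of one early tablet is a debatable change to the gatekeeping endpoint, which has only 87% planned power. If such a rule were primary and the planned rates count users as successes, 5% use on LE and 2% on vehicle would give 82.4% power with users clearing at the arm rate. If all users clear, the rates are 23.3% vs 12.3% and power is 73.0%; with the two shares reversed it is 98.7%. That belongs in a sensitivity analysis.

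**Unseen text.** Sections 8.1.2 and 8.5.1.1 refer to a separate Statistical Analysis Plan that is not in the supplied document. A scoring rule could be there.

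**Conclusion.** The gap is real in the text supplied. A subject who takes a disallowed analgesic for study-eye pain before Visit 5, is not withdrawn and reports Grade 0 is a success on the primary pain endpoint. The safeguards are discretionary, supportive or partial.

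The size is modest and rests on an assumed U of 2% to 5% and on assumed Grade 0 rates among users. The shift is about 0.5 to 3 points on 25.3, in either direction, and nil if use is equal and every user is Grade 0. A reader might infer that the pain result or its power is in danger. The calculations do not support this, since power is at least 98.9% in every case shown. Nor do the documents show that the current rule favours LE gel. The reason to act is a clearly defined endpoint and a pain estimate free of another drug's effect, settled before unmasking.

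**What to change.** **Primary pain endpoint.** Add to 8.5.1.1 and 8.5.9: a subject who takes an NSAID or COX-2 inhibitor, acetylsalicylic acid above 81 mg/day, an opioid or propoxyphene for study-eye pain between the first dose and the Visit 5 assessment is a failure on the primary pain endpoint. Indication and missing dates are settled in the masked deviation review (8.5.6). The date imputation in 8.5.4 is not used for this purpose, because it would place a wholly undated record on the first day of treatment. The rule does not by itself require withdrawal.

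**Primary AC-cell endpoint.** Leave the scoring unchanged.

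**One sensitivity analysis of both primary endpoints.** Count any disallowed analgesic or anti-inflammatory use in the same window as failure whatever the indication. For AC cells, restrict this to NSAIDs, COX-2 inhibitors, acetylsalicylic acid above 81 mg/day and corticosteroids.

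**Cost.** Text in two places and one extra analysis. Section 6.3 already collects medications and their indications, and the masked review is already planned; it gains one task. Pain success rates fall slightly in all arms. A subject with brief early use who is truly pain-free at Day 8 is scored a failure. Acetaminophen is permitted, so Grade 0 reached with its help still counts as success.

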#### 6.2.4     Lost to Follow-up

Subjects who do not return for scheduled follow-up visits, as defined by the visit window, and who cannot be contacted after at least 2 attempts may be considered lost to follow-up. All follow-up attempts will be documented and kept with the subject's source documentation, and the applicable eCRFs will be completed.

### 6.3     Concomitant Medications/Therapy

Administration of all medications used up to 30 days prior to study entry (ie, date ICF signed) through study exit must be recorded in the source documentation and in the appropriate section of the Concomitant Medications eCRF. Indications for these medications should be recorded in the subject's Medical History eCRF or Adverse Event eCRF, as applicable. Medication used intraoperatively will be recorded only in source documentation (also refer to [Section 6.3.1](#)).

### 6.3.1 Permitted Therapy

With the exception of the disallowed medications specified in the eligibility criteria ([Section 3.2.1](#)) and in [Section 6.3.2](#), any medications that, in the Investigator's judgment, will not interfere with the study parameters are allowed to be used concurrently. For example, the following medications listed in [Table 1](#) are permitted:

**Table 1: Permitted Therapies**

Medication/Class of Drug	Status
Acetaminophen	Permitted
Acetylsalicylic Acid $\leq$ 81 mg/day	Permitted
Anesthetic Agents a	Permitted for surgery, IOP, and fundus examination ONLY
Antibiotic, Intracameral Injection at end of surgery b	Permitted
Antibiotic, Topical (NOT combined with a steroid) c	Permitted
Anti-Cholesterol Medications	Permitted
Antidepressants	Permitted
Antihypertensive Agents	Permitted
Antimicrobials, Systemic	Permitted
Birth Control Pills	Permitted
Cardiovascular Agents	Permitted
Epinephrine/Noradrenaline	Permitted for surgery ONLY
Estrogen Therapy	Permitted
Oral Histamine H 2 Receptor Antagonist (example: Zantac)	Permitted
Hypoglycemic Agents	Permitted
Hypotensive Medication, topical ocular	Permitted for one-time use at Day 1 post-op (Visit 3)
Insulin	Permitted
Mydriatic Agents a	Permitted for surgery and fundus examination ONLY
Neosynephrine/Phenylephrine	Permitted for surgery and fundus examination ONLY
Thyroid Preparations	Permitted

a Standard anesthetic and mydriatic agents may be used intraoperatively and for IOP and fundus examination ONLY.

b Intracameral injection of antibiotic is allowed at the end of surgery.

c Use of topical antibiotics is allowed if they are not used in combination with any steroid (eg, Zylet® or TobraDex should not be used).

**NOTE: Intraoperative use of topical antibiotics or other standard of care surgical medications should be recorded in the source documentation only. Topical antibiotics used preoperatively or postoperatively should be recorded in the Concomitant Medications eCRF provided by the Sponsor.**

Subjects requiring post-surgical treatment rescue will be considered treatment failures and subjects will stop use of study drug. Document all rescue medication use in the eCRFs.

Please refer to [Section 6.2.3.1](#) Rescue Medication on page 41 for Early Term Visit

